**The Role of Narrow Band Imaging (NBI)
Bronchoscopy in Detecting Bronchial Squamous
Dysplasia in Lung Cancer**

[name]

**Department of Pulmonology and Respiratory Medicine, Persahabatan
Hospital, Faculty of Medicine Universitas Indonesia**

ID: ND-552/UN2.RST/PPM.00.00/2023

October 26th, 2023

1. Title

The Role of Narrow Band Imaging (NBI) Bronchoscopy in Detecting Bronchial Squamous Dysplasia in Lung Cancer

2. Ethical clearance

The date of approval from Health Research Ethics Committee Faculty of Medicine Universitas Indonesia, [name] General Hospital is 23rd March 2023 (KET-361/UN2.F1/ETIK/PPM.00.02/2023)

3. Study Protocol

- Problem Statement

1. What are the NBI imaging criteria for detecting bronchial squamous dysplasia in lung tumor patients?
2. How does the diagnostic profile of NBI bronchoscopy compare with standard bronchoscopy (white light bronchoscopy, WLB) in detecting bronchial squamous dysplasia in lung tumor patients?
3. Can the addition of NBI to standard bronchoscopy procedures improve diagnostic accuracy in detecting bronchial squamous dysplasia in lung tumor patients?

- Research Objectives

This research aims to determine the diagnostic profile (area under the curve, AUC; sensitivity, specificity, positive predictive value, and negative predictive value) of NBI bronchoscopy in detecting bronchial squamous dysplasia in lung tumor patients.

4. Method

- Study Design

This is an observational diagnostic study. The research was conducted at the bronchoscopy suite of Persahabatan Hospital, where bronchoscopy procedures, bronchial biopsy collection, and specimen handling took place. The histopathological examinations were carried out in the Department of Anatomical Pathology, Faculty of Medicine, Universitas Indonesia, The patient recruitment time ranges from March to December 2023.

- Population

The target population consists of all lung tumor patients. The accessible population consisted of lung tumor patients who underwent bronchoscopy procedures at Persahabatan Hospital from March to December 2023.

- Study participants

- The study participants comprised individuals from the accessible population who met the research participants acceptance criteria and provided informed consent. The consecutive sampling method was employed.
- **Study participants calculation**

The study participants size was calculated using the diagnostic research sample size formula. The minimum sample size required was 110 participants

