 - **Inclusion criteria**
 1. Patient aged > 18 years undergoing bronchoscopy for diagnostic evaluation of lung tumors
 2. Recent radiological examinations, including both chest X-ray and chest CT scans, within the last month, revealed a central lesion of lung cancer
 - **Exclusion criteria**
 1. Refusal to provide informed consent
 2. Contraindications to bronchoscopy
 - **Participants selection**

Screening was conducted on all lung tumor patients scheduled for bronchoscopy procedures, and the participants selection was carried out in accordance with the inclusion and exclusion criteria
 - **Sampling Technique**

The preparation and execution of bronchoscopy and bronchial biopsy were performed in accordance with the standard operating procedures (SOP) at Persahabatan Hospital. The bronchoscopy and bronchial biopsy procedures were conducted by a single operator, the principal investigator. The bronchoscopy procedure uses general anesthesia. The flexible fiberoptic bronchoscopy was performed using an Olympus EVIS EXERA III with a Xenon light source, model CLV-190, and BF-1TQ170 series scope. The Boston Scientific Radial Jaw™ 4 disposable lung biopsy forceps were employed. Bronchoscopy was initially performed under the white light, followed by the activation of the NBI feature for airway inspection. Biopsies were obtained from areas identified through NBI bronchoscopy findings. Furthermore, the criteria for bronchoscopy images suspected for dysplasia included the presence of dotted vessels, capillary loops, tortuous vessels, and abrupt ending vessels. No biopsies were conducted on infiltrative neoplasms or tumors. The biopsied tissue was then preserved in a separate 10% formalin solution. Tissue processing involved paraffin embedding and Hematoxylin-Eosin staining. Tissue processing was performed using a Tissue Processor machine. Following tissue processing, paraffin blocks were created and sectioned. Hematoxylin-Eosin staining was then performed. Diagnosis of squamous bronchial dysplasia (pre-cancer lesion) was made by a specialist in Anatomical Pathology.

5. Statistical Analysis Plan (SAP)

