The research data were recorded on research forms and subsequently entered into SPSS 26 software. the bivariate analysis was conducted between each vascular pattern based on NBI bronchoscopy and the histopathological result. The descriptive data will be presented by the text and tables consist of the basic characteristics of the study participants and research variables. The multivariate analysis was performed on all vascular patterns based on NBI bronchoscopy and histopathological results. Furthermore, a pre-cancer prediction score was generated. An analysis of the AUC (area under the curve) of the squamous dysplasia prediction model form NBI bronchoscopy findings was conducted with a significance level set at $p < 0.05$

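### Does leaving the unit of analysis unstated (biopsied area or patient) undermine the pattern tests, the prediction score and the AUC?

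*Combined protocol and SAP*

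**What the plan says.** Section 4, Sampling Technique, gives the biopsy rule: "Biopsies were obtained from areas identified through NBI bronchoscopy findings". Suspicion rests on "the presence of dotted vessels, capillary loops, tortuous vessels, and abrupt ending vessels". The only stated limit is "No biopsies were conducted on infiltrative neoplasms or tumors", which says nothing about how many areas one patient may contribute. On specimens the text says "The biopsied tissue was then preserved in a separate 10% formalin solution". That could mean separate by area, separate by patient, or separate from other tissue. The procedure also follows the hospital's standard operating procedures, which are not part of the document.

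Section 5, the whole SAP, says "the bivariate analysis was conducted between each vascular pattern based on NBI bronchoscopy and the histopathological result", then "The multivariate analysis was performed on all vascular patterns based on NBI bronchoscopy and histopathological results", then "Furthermore, a pre-cancer prediction score was generated", followed by an AUC analysis at the 0.05 level. It names no row unit, no rule for combining areas and no method for correlation within a patient.

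Section 4 counts the study in people: "The minimum sample size required was 110 participants". The objective in section 3 is also framed in terms of patients.

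**The concern.** A vascular pattern and a histology result both belong to a place in the airway, while the sample size counts people. If some patients gave several areas, both obvious analyses have a weakness.

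- **One row per area, ordinary tests.** Areas from one patient tend to resemble each other. Treating them as independent can misstate standard errors, p-values and the AUC interval.
- **One row per patient, any pattern against any dysplasia.** This removes the correlation and is a legitimate patient-level definition. It can, however, credit a pattern seen in one place with dysplasia found in another, which suits a pattern-based score poorly.

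The pattern tests feed the multivariate model, the model feeds the score, and the score feeds the AUC. An ambiguous unit would therefore run through every planned inference.

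**Working it through.** **The plan's own figure.** The 110 cannot be reproduced, because section 4 gives no expected accuracy, precision or prevalence. With the single-proportion formula n = z²p(1−p)/(d² × prevalence), 14 of 720 assumed input sets fall within 3% of 110. For example, p = 0.85, d = 0.08 and prevalence 0.70 give 1.96² × 0.1275/(0.0064 × 0.70) = 109.3, rounded up to 110. With p = 0.90, d = 0.08 and prevalence 0.50 the result is 109. So the 110 does not show which unit was intended.

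**Assumptions.** The documents give neither areas per patient (m) nor the ICC. I take m = 2 to 3 and ICC = 0.1 to 0.5, with m = 1 as the reference.

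**Proportions such as the PPV.** The design effect is DE = 1 + (m−1) × ICC. The true standard error is √DE times the naive one, and coverage of a nominal 95% interval is 2Φ(1.96/√DE) − 1.

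| m | ICC | DE | SE ratio | Coverage |
|---|---|---|---|---|
| 1 | any | 1.0 | 1.00 | 95.0% |
| 2 | 0.1 | 1.1 | 1.05 | 93.8% |
| 2 | 0.3 | 1.3 | 1.14 | 91.4% |
| 2 | 0.5 | 1.5 | 1.22 | 89.0% |
| 3 | 0.1 | 1.2 | 1.10 | 92.6% |
| 3 | 0.3 | 1.6 | 1.26 | 87.9% |
| 3 | 0.5 | 2.0 | 1.41 | 83.4% |

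**Pattern against histology, nominal 5% chi-square.** Here the clustering of the pattern matters as well: DE ≈ 1 + (m−1) × ICC(pattern) × ICC(histology). With histology ICC 0.3 and a pattern constant within patient, DE is 1.3 (m = 2) or 1.6 (m = 3), and the true error 2(1 − Φ(1.96/√DE)) is 8.6% or 12.1%. Simulation with 110 patients and an assumed dysplasia rate of 30% (20,000 runs; 5,000 for the contrasting case) gives:

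| Pattern within patient | Naive error, m = 2 | Naive error, m = 3 |
|---|---|---|
| Unclustered | 4.7% | 5.2% |
| ICC 0.5 | 6.4% | 8.5% |
| Constant | 8.7% | 12.3% |
| Contrasting | 1.9% | 2.9% |

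Patient-clustered robust tests stayed at 4.8% to 5.4% throughout. A four-pattern logistic model at pattern ICC 0.5 (4,000 runs) gave 6.9% and 8.5% per pattern with ordinary errors, and 5.5% and 5.4% with robust errors.

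**AUC near 0.76 (4,000 runs).** With an unclustered score, naive 95% coverage is 94.4% (m = 2) and 94.1% (m = 3). It falls to 90.7% and 87.7% only with a score ICC of 0.9 and a latent-scale histology ICC of 0.5. That latent value is about 0.32 on the observed yes/no scale at 30% prevalence, so it is not on the same scale as the 0.3 used for the chi-square. The score ICC of 0.9 is extreme.

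**Collapsing to any pattern against any dysplasia.** Assume pattern prevalence 50%, dysplasia 40% with the pattern and 14% without, and independent areas. The area-level OR is (0.40/0.60)/(0.14/0.86) = 4.10. For m = 2:

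- any pattern, no dysplasia: 0.73² − 0.43² = 0.348
- any pattern, any dysplasia: 0.75 − 0.348 = 0.402
- no pattern, no dysplasia: 0.43² = 0.1849
- no pattern, any dysplasia: 0.25 − 0.1849 = 0.0651
- OR = (0.402 × 0.1849)/(0.348 × 0.0651) = 3.28
- pattern and dysplasia only at different areas: 2 × 0.30 × 0.07 = 0.042, and 0.042/0.402 = 10.4%

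For m = 3 the OR is 3.19 and the share is 13.7%.

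**Which unit do the documents suggest?** The plural areas can run across 110 people as easily as within one person. The sample size counts participants, the objective speaks of patients, and the SAP sets each pattern against one histopathological result, in the singular. These point towards one row per patient without proving it. Nothing points to several areas per patient except the absence of a cap.

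**The case for a change.** The strongest case for a change is that the gap itself is certain. Participants in the sample size is only a hint, and a patient-level analysis of several areas would still need a combining rule. That rule has consequences: with an assumed 20% dysplasia rate per area and independent areas, an any-area rule gives 1 − 0.8² = 36% with two areas and 1 − 0.8³ = 49% with three, which moves the PPV and NPV. The first question in the Problem Statement, which NBI criteria detect dysplasia, also needs each pattern tied to the histology of the same place. One sentence would settle the matter.

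The omission stands, and so does the value of stating the unit and the number of areas per patient when results are reported. The harm does not follow from the text. It needs several areas per patient, which is undocumented, and also an ordinary area-level analysis or an unsuitable way of collapsing areas. Even then the error in the pattern tests has no fixed direction: 1.9% to 12.3%, and close to nominal when patterns do not cluster. Several areas can therefore give wrong standard errors, but need not.

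Nor would every repair work. If the link between pattern and histology was lost, choosing one index area per patient would not help, because its histology could not be identified. Only a labelled patient-level summary, or patients with a single area, would remain.

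**Conclusion.** No change to the plan follows. This is a missing definition that analysts fill from the data: either patient identifiers repeat in the data set or they do not. If each appears once, DE = 1 and the effect on every planned analysis is zero. If some repeat and each pattern is linked to its own histology, the usual handling is a logistic model by generalised estimating equations, clustered on patient, with patients resampled for PPV and AUC intervals. In the simulations, patient-clustered robust errors kept the chi-square tests at 4.8% to 5.4% and the four-pattern model at 5.4% to 5.5%. The plan's silence rules none of this out.

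The possible size, if areas were treated as independent, is coverage of 93.8% down to 83.4% for proportions and a test error of 1.9% to 12.3%. These ranges rest on an assumed m of 2 to 3, an ICC of 0.1 to 0.5 for proportions, and a histology ICC of 0.3 with 30% dysplasia for the tests. None of these values is in the documents. The hospital procedures, which might fix the number of biopsies and the labelling, are not included. The conclusion would be different if the record showed several areas per patient analysed as independent rows.

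### The prediction score's AUC is estimated and tested in the same patients who set its weights, so it is biased upward and, if tested against 0.5, the 0.05 level does not hold

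*Combined protocol and SAP*

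**What the plan says.** Section 5 (SAP) is one paragraph and sets out a sequence. Each vascular pattern is first compared with histology on its own. Then "The multivariate analysis was performed on all vascular patterns based on NBI bronchoscopy and histopathological results". Then: "Furthermore, a pre-cancer prediction score was generated". Last: "An analysis of the AUC (area under the curve) of the squamous dysplasia prediction model form NBI bronchoscopy findings was conducted", with significance set at p<0.05.

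Section 4 gives the data for all of these steps. "The consecutive sampling method was employed", and "The minimum sample size required was 110 participants". Four candidate patterns are named under Sampling Technique: "the criteria for bronchoscopy images suspected for dysplasia included the presence of dotted vessels, capillary loops, tortuous vessels, and abrupt ending vessels".

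The objective in section 3 puts AUC first among its measures: "This research aims to determine the diagnostic profile (area under the curve, AUC; sensitivity, specificity" and the predictive values.

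The documents mention no second cohort, data split, cross-validation, bootstrap or shrinkage, and no weights fixed in advance. They do not state the model type, any selection rule, the point-assignment rule, the null value for the AUC or the sidedness of the test.

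**The concern.** A fitted model chooses its weights to agree as well as possible with the outcomes in hand. Its AUC on those same outcomes is therefore biased upward as an estimate of performance in new patients. The usual test of AUC = 0.5 assumes a marker fixed before the outcomes were seen. A fitted score breaks that assumption, so the nominal 5% error rate no longer applies.

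This affects the main result. AUC is the first measure in the objective, and the AUC of this model is the only performance analysis the SAP specifies. If the patterns carry signal, the reported value overstates what the score will do elsewhere, most of all when the score is weak or dysplasia cases are few. If they carry none, p<0.05 will still be reached far too often.

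**Working it through.** **The plan's own figure.** The documents give no inputs for 110, so it can be neither reproduced nor called wrong. With the common formula n = z²·p(1−p)/d² ÷ prevalence, unrelated inputs all land there:
- sensitivity 0.80, d 0.15, prevalence 0.25: 1.96²×0.16/0.0225 = 27.3, and 27.3/0.25 = 109.3, so 110;
- sensitivity 0.85, d 0.08, prevalence 0.70: 1.96²×0.1275/0.0064 = 76.5, and 76.5/0.70 = 109.3, so 110.

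No prevalence can be recovered from it, so a range is used below.

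**Inputs from the documents.** n = 110, four patterns, significance level 0.05, one sample.

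**Assumptions.** Logistic regression; dysplasia prevalence 15-50% (10-50% where noted); a two-sided test of AUC = 0.5. Patterns are coded either as four free binary variables (frequencies 0.35/0.30/0.30/0.20) or as one predominant pattern per patient (3 df).

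**Why the level fails.** With no association, the squared standardised difference of the best-fitting linear score behaves roughly like a chi-square on k df, where k is the number of fitted terms. The test compares it with 1.96² = 3.84, the cut-off for 1 df. With 3.84/2 = 1.92:
- k = 4: e^(−1.92)×(1+1.92) = 0.43;
- k = 6: e^(−1.92)×(1+1.92+1.92²/2) = 0.70.

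The approximation does not involve n, so a larger sample should not help. Simulation agrees on both counts.

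**No true association, simulated studies, n = 110 unless stated**

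| Setting | Rejects AUC = 0.5 |
|---|---|
| Four free patterns, all entered, tie-corrected rank test | 38-41% |
| Same, DeLong variance | 40-47% |
| Same, rank test, n = 200 and n = 400 | 39-41% |
| One predominant pattern, all entered, rank / DeLong | 22-24% / 25-28% |
| Bivariate screen at p<0.25 | 26-33% |
| Backward selection, four free patterns | 17-27% |
| Backward selection, one predominant pattern | 12-22% |

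Full-entry cells used 4,000 runs at n = 110 and 2,000 at n = 200 and 400; selection cells used 1,200-2,500. Mean apparent AUC with full entry was 0.58-0.64 against a true 0.50.

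A separate simulation with pattern frequencies of 20-40% and prevalence 10-50% gave 35-42% for four patterns. At 30% prevalence it gave 26% for three patterns and 68% for six, and 42% for a four-pattern score rounded to points.

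**Controls.** A score with equal weights fixed in advance rejected in 4.3-5.0% of null studies. The joint likelihood-ratio test of the full model rejected in 4.6-7.1%. The inflation therefore comes from fitting and testing on the same data.

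**Real signal, four free patterns, 1,500 runs per cell**

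| Best attainable AUC | Apparent minus new-patient AUC |
|---|---|
| 0.61 | 0.07-0.11 |
| 0.67 | 0.05-0.09 |
| 0.75 | 0.03-0.05 |

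The larger gap in each row is at 15% prevalence (110×0.15 = 16.5, about 17 cases). The separate simulation gave 0.04-0.13 for weak to moderate signal and 0.01-0.07 for strong signal.

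**After bootstrap correction.** With log odds ratio 1 per pattern and 30% prevalence, mean apparent AUC 0.758 became 0.721, against a true 0.715. With no signal at the same prevalence, 0.609 became 0.530, so some optimism remains.

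**The case against.** The strongest case on the other side has four parts.

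1. The SAP never states the point rule. If every pattern simply scored one point, the test would hold its level (3.8-5.4% in null runs). This is possible for the score, but the AUC sentence names the prediction model, which is fitted, and nothing says the weights are preset.

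2. The false-positive figures need two conditions: that the p-value tests AUC = 0.5, and that no pattern is informative. The patterns were chosen as signs of suspected dysplasia, so a complete absence of signal is a limiting case. With the two stronger signals the test passes in 89-100% of studies and its error rate matters little. This stands, and the error rates should be read as conditional. The bias in the estimate does not depend on either condition.

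3. The bias is an average. With those signals the apparent AUC fell below the new-patient AUC in 11-25% of studies, and for a strong signal the bias (0.03-0.045) is below one standard deviation of the apparent AUC (0.04-0.06). This also stands. However, a confidence interval around the apparent AUC would not remove a systematic shift.

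4. The unit of analysis is not stated. If several biopsy sites per patient are analysed, an ordinary likelihood-ratio test rejects in 8-10% of null studies (2-3 sites, assumed within-patient correlation 0.5). Resampling whole patients covers this for the bootstrap but not for the joint test, so the remedy must allow for it.

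**Conclusion.** The concern holds. Evaluating the model in its own development data is an inference, but it is the only reading the text supports: one sample, one fitted model, one score, then its AUC. Followed as written, the plan gives an AUC that is biased upward in expectation.

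If the null is 0.5, the chance of p<0.05 for a worthless score is 12-47% over the codings and selection rules examined, and 22-47% with all patterns entered, the closest reading of the SAP. With real signal the main gap is 0.03-0.11. These sizes rest on assumed prevalence, pattern frequencies, coding and effects; the direction does not. Because this is the SAP's only specified performance result, it should be corrected before the AUC is reported.

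**What to change.** Amend section 5 as follows.

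1. State the unit of analysis, the model, any selection rule, the point-assignment rule and the null hypothesis. The resampling cannot be reproduced without them.
2. Replace the p-value on the in-sample AUC by a joint likelihood-ratio test of all candidate pattern terms, with df equal to the number of terms fitted, done before any selection. If more than one site per patient is analysed, use a version that allows for clustering.
3. Report as the headline a bootstrap optimism-corrected AUC with a 95% confidence interval, naming the interval method. Resample patients, and repeat all fitting, selection and score building in each resample. Say in advance how separation will be handled: at 15% prevalence about 5% of null fits had a coefficient beyond 8.
4. Label the in-sample AUC as apparent.
5. State that the correction deals with overfitting only. Biopsies came from areas identified by NBI, so the result applies to sites chosen in that way.

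The cost is a short script and a few lines of text, with no new patients or biopsies. The reported AUC will be somewhat lower. The joint test is also harder to pass: with log odds ratio 1 per pattern it rejected in 60%, 93% and 99% of studies at prevalence 10%, 30% and 50% (150 runs each, so imprecise). Some optimism survives correction: about 0.54 when the truth is 0.50, 0.59-0.60 against 0.56-0.58 for a weak score, and 0.02 or less for a strong one. The corrected AUC should therefore accompany the joint test and not replace it.

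### The objective promises sensitivity, specificity, PPV and NPV, but the SAP names only the AUC of a score built on the same data and states no test-positive rule

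*Combined protocol and SAP*

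**What the plan says.** Section 3 (Research Objectives) sets the aim as the "diagnostic profile (area under the curve, AUC; sensitivity, specificity, positive predictive value, and negative predictive value) of NBI bronchoscopy" for detecting squamous dysplasia. That is five measures.

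Section 5 (SAP) lists, besides descriptive tables:

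- a per-pattern step: "the bivariate analysis was conducted between each vascular pattern based on NBI bronchoscopy and the histopathological result";
- a joint model: "The multivariate analysis was performed on all vascular patterns based on NBI bronchoscopy and histopathological results";
- a score: "Furthermore, a pre-cancer prediction score was generated";
- the assessment of that score: "An analysis of the AUC (area under the curve) of the squamous dysplasia prediction model", at a 0.05 significance level.

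Sensitivity, specificity, PPV and NPV do not appear in section 5. Nor does a score threshold, a way of choosing one, or any validation.

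The nearest thing to a positivity rule is in section 4 (Sampling Technique), where the "criteria for bronchoscopy images suspected for dysplasia included the presence of dotted vessels, capillary loops, tortuous vessels, and abrupt ending vessels". The text does not say whether one, several or all of these are needed, and does not tie the list to any accuracy estimate.

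**The concern.** An AUC summarises a score over all its cut-offs and needs none. Each of the other four measures exists only once a result has been declared positive or negative. A plan that stops at the AUC therefore leaves four of the five promised measures without a defined calculation.

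The usual way to fill such a gap is to read a cut-off from the ROC curve of the score just fitted. The same participants would then have supplied the weights, the cut-off and the accuracy figures. Sensitivity and specificity obtained this way are biased upwards, and a reader who does not know how the cut-off arose cannot discount them.

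**Working it through.** **1. Count.** Promised in section 3: AUC, sensitivity, specificity, PPV, NPV = 5. Named in section 5: AUC = 1. Not named: 5 − 1 = 4.

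**2. Does the sample size imply a cut-off or a target?** The only figure in the plan is a minimum of 110 participants, from an unnamed diagnostic formula with no inputs. It can be neither reproduced nor refuted. With n = z²·Se(1 − Se)/d², an assumed Se of 0.80 and half-width d of 0.075 give 1.96² × 0.16 / 0.005625 = 109.3, rounded up to 110. With a prevalence divisor, Se 0.85, d 0.08 and prevalence 0.70 also give 110. No operating point can be inferred from it.

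**3. Does the AUC fix the other four?** Assume an equal-variance binormal ROC curve, AUC 0.80 and prevalence 30% (the documents give neither value). Then Se = 1 − Φ(z_Sp − √2·Φ⁻¹(0.80)), with √2 × 0.8416 = 1.190.

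| Specificity | Sensitivity | PPV | NPV |
|---|---|---|---|
| 0.50 | 0.88 | 0.43 | 0.91 |
| 0.70 | 0.75 | 0.52 | 0.87 |
| 0.90 | 0.46 | 0.67 | 0.80 |

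For example, the PPV at specificity 0.90 is 0.464 × 0.3 / (0.464 × 0.3 + 0.1 × 0.7) = 0.67. One AUC is compatible with very different profiles.

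**4. Operating points of a simple pattern count.** Assume four independent patterns, each present in 60% of dysplastic and 30% of other areas, with at least one present in every biopsied area. The denominators are 1 − 0.4⁴ = 0.9744 and 1 − 0.7⁴ = 0.7599.

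- At least two: Se = 0.8208/0.9744 = 0.84; Sp = 1 − 0.3483/0.7599 = 0.54; Youden index 0.384.
- At least three: Se = 0.4752/0.9744 = 0.49; Sp = 1 − 0.0837/0.7599 = 0.89; Youden index 0.378.
- All four: Se = 0.1296/0.9744 = 0.13; Sp = 1 − 0.0081/0.7599 = 0.99.

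**5. Optimism when the cut-off is picked on the same data.** Simulated studies of 110, taking one biopsied area per participant (the documents do not state the unit), with the Youden-best cut-off chosen in sample and compared with its true performance:

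- *Simple count*, about 40% dysplasia: sensitivity plus specificity is overstated by about 0.01 to 0.05 across a range of pattern frequencies. Examples are 0.011 at 50% v 20%, 0.018 at 60% v 20% and 0.044 at 50% v 40%.
- *Fitted four-pattern score*, which is closer to what the SAP describes: about 0.09 to 0.16 under assumed pattern frequencies. The gap shrinks as the patterns separate better. A separate set-up does not require a pattern to be present, and uses prevalence 20% to 50% and log odds ratios per pattern from 0 (uninformative) to 1. It gave about 0.10 to 0.25.

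**6. Stability of the chosen cut-off.** At 60% v 30%, where the two Youden values nearly tie, the choice between at least two and at least three patterns split about evenly. Elsewhere it was 70/30 (50% v 30%), 87/13 (60% v 20%), 94/6 (50% v 20%) and 8/92 (70% v 40%).

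**The case against.** The strongest reply is that the plan is not confined to the AUC. Each vascular pattern is naturally present or absent, so the bivariate step can give a 2x2 table, and all four measures, without a score cut-off. That stands: the AUC is the only accuracy measure named, not the only analysis. It does not close the gap. The SAP does not say what the bivariate step will report, and the objective concerns NBI as a test, not four signs taken singly.

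It is also fair that deriving NBI criteria is itself a stated question (Problem Statement 1). A data-derived cut-off is therefore legitimate if it is labelled as such and its optimism is corrected.

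Four stronger readings are tempting, and the documents do not support them:

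- *Every biopsy is NBI-positive by construction if any one pattern suffices.* Biopsy sites were chosen on what NBI showed, but the text says the criteria included the four patterns. It does not say that every sampled site met the list or that the list is complete. If it were so, the defect would be selective verification, which no cut-off cures.
- *Reported sensitivity will flip between 0.84 and 0.49 by chance.* The even split belongs to one near-tied setting and is not a general result.
- *A particular count, such as two or more, is the right rule.* Nothing in the documents favours one count, and at some assumed frequencies three or more does better.
- *A fixed cut-off would rescue the comparison with white light bronchoscopy.* That comparison fails for other reasons: the SAP contains no WLB analysis, and biopsies are directed by NBI.

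**Conclusion.** The mismatch is real and needs no calculation to establish: four of the five promised measures are absent from the SAP, and no test-positive result is defined. It should be corrected.

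The size of the resulting bias is conditional. If a cut-off is taken from the same ROC curve at n = 110, sensitivity plus specificity is overstated by about 0.01 to 0.05 for a plain count and about 0.09 to 0.16 for a fitted four-pattern score. The chosen operating point can also be unstable when cut-offs are nearly tied. These figures assume independent patterns, a Youden rule and pattern frequencies that the documents do not give.

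A reader might infer that the investigators did choose a cut-off after seeing the data. The documents do not show this; they only leave it open.

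**What to change.** Add to section 5: sensitivity, specificity, PPV and NPV, each with a 95% CI and explicitly among biopsied areas, are reported

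- for each vascular pattern, present against absent;
- at every pattern count (at least one, two, three, all four);
- at every value of the generated score. Four binary patterns give at most 2⁴ = 16 combinations, so the table stays short.

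No cut-off is called optimal unless the investigators fixed it, with their reasons, before histology was linked. Any cut-off derived from the ROC curve is labelled exploratory and reported with a bootstrap optimism correction that repeats both the model fit and the choice of cut-off.

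The document is dated October 26th, 2023, within the March to December 2023 recruitment period, and describes its methods in the past tense, so prior fixing may no longer be possible. The full table works either way.

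The cost is SAP wording, one table from data the planned analyses already need, and a bootstrap. The figures will look less favourable than at a data-picked cut-off. The change does not make up for the lack of biopsies from NBI-negative areas and does not restore the WLB comparison.
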